- m. Plasma PK samples will be collected via sparse sampling from approximately 30 patients (who give optional consent) in a 2:1 ratio to assess the PK of MP1032 on Day 1 (single dose) and Day 7 (steady state). A total of 16 samples will be collected relative to the first dose on Day 1 and the first dose on Day 7. Samples on Day 1 and Day 7 will be collected predose (within 10 minutes before the first daily dose) and postdose at 10 minutes, 20 minutes, 30 minutes, 60 minutes, 8 hours (before next dose), and 24 hours before the next morning dose (if applicable), if possible. Patients who provide consent for the PK sampling, but are no longer hospitalized on Day 7, will not have Day 7 PK samples collected.

MetrioPharm AG	MP1032-CT05
MP1032	Protocol v2.0 - Bulgaria

- n. Blood samples to be obtained on Day 1 (before the first study drug administration) and Days 7, 14, 21, 28, and 60. Blood samples for biomarkers must be collected on Days 7, 14, 21, 28, and 60 if a patient is still hospitalized. If a patient is discharged, the study site should arrange an outpatient visit (ie, at the study site) to accommodate the collection of blood samples for biomarkers on Days 7, 14, 21, 28, and 60.
- o. To standardize the assessment of COVID-19 severity, respiratory rate, SpO₂, and heart rate will be measured when the patient is on room air at sea level (ie, no supplemental oxygen, if possible) and at rest for at least 5 minutes. If possible, the site should collect the information from each patient at the same time each day (±1 hour).
- p. Record the patient's clinical status related to COVID-19 on the NIAID 8-point ordinal scale and also record the date and time for each individual component of the NIAID 8-point ordinal scale including: invasive or non-invasive mechanical ventilation/ECMO start/stop, high-flow/mask oxygen start/stop, supplemental oxygen start/stop (nasal cannula, liter flow [and its conversion to FiO₂], other delivery services), hospital discharge (whether with limitations or without limitations), hospitalization type (eg, transfer to ICU) start/stop, and (if applicable) death, cause of death (including relatedness to COVID-19), and date/time of death. If possible, the site should collect the information from each patient at the same time each day (±1 hour).

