10.2 Study Procedures

Assessments and their timing are to be performed as outlined in the Schedule of Assessments (Table 1). Section 12.5 specifies clinical laboratory assessment samples to be obtained.

Assessments and procedures scheduled at a visit where study drug is administered should be performed before administration of treatment unless otherwise indicated in the Schedule of Assessments (Table 1).

Efficacy assessments are described in Section 11 and include COVID-19 symptoms, COVID-19 severity, clinical status related to COVID-19 on the NIAID 8-point ordinal scale, HRQoL assessed by the EQ-5D-5L questionnaire (Appendix 2), and COVID-19 testing.

Safety assessments are described in Section 12 and include medical/surgical history and demographics, vital signs, physical examinations, ECGs, clinical laboratory assessments, and AEs. PK assessments are described in Section 13 and include PK sampling and PK analytical methodology. Biomarkers are described in Section 14.1.

The investigator may, at his/her discretion, arrange for a patient to have an unscheduled assessment, especially in the case of AEs that require follow-up or are considered by the investigator to be possibly related to the use of study drug. The unscheduled visit page in the eCRF must be completed.

Procedures for early study withdrawal are described in Section 8.4.

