12.6.6 Overdose

MP1032

The investigator must immediately notify Syneos Health of any occurrence of overdose with the study drug.

PHARMACOKINETICS B

B1 Pharmacokinetic Sampling

Blood samples for PK analysis of MP1032 plasma concentrations will be collected at the time points indicated in the Schedule of Assessments (Table 1) from a PK subset of approximately 30 patients (who give optional consent). In summary, PK samples will be collected via sparse sampling from these 30 patients (approximately) in a 2:1 ratio (approximately 20 patients from the 300 mg MP1032 BID plus SoC group and approximately 10 patients from the placebo group plus SoC group) to assess the PK of MP1032 on Day 1 (single dose) and Day 7 (steady state). A total of 16 samples (approximately 4.9 mL per time point for a total of approximately 78.4 mL) will be collected relative to the first dose on Day 1 and the first dose on Day 7. Samples on Day 1 and Day 7 will be collected predose (within 10 minutes before the first daily dose) and postdose at 10 minutes, 20 minutes, 30 minutes, 60 minutes, 120 minutes, 8 hours (before next dose), and 24 hours before the next morning dose (if applicable), if possible. Patients who

This document is confidential.

Page 67 of 89

MetrioPharm AG	MP1032-CT05	
MP1032	Final	
MetrioPharm AG	MP1032-CT05	
MP1032	Protocol v2.0 - Bulgaria	

provide consent for the PK sampling, but are no longer hospitalized on Day 7, will not have Day 7 PK samples collected.

For patients in the PK subset on Day 1 and Day 7 only: Patients should not eat within the 4 hours before planned study drug administration and within the 120 minutes after study drug dosing, when feasible. Thus, study drug should be administered in fasted state (\geq 4 hours), when feasible. However, if a patient has eaten within the 4 hours before their planned administration, study drug dosing may proceed. The patient's fed or fasted state, as well as food intake (yes/no) within the 120 minutes after study drug dosing should be recorded. The PK samples should be collected as planned regardless of the patients' fasted/fed state. The study site should record the date and time of dosing (recorded as the time when the first capsule is administered).

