15.5 Pharmacokinetic Analysis

The PK parameters (such as C_{max}, T_{max}, AUC_{0-t}, and others) of MP1032 on Day 1 (single dose) and Day 7 (steady state; if available), using up to 8 hours postdose, will be derived applying noncompartmental analysis. PK parameters will be summarized along with plasma concentrations at various time points. Individual and mean plasma concentration versus time will be presented on linear, and semi-log scales. Further details of the PK analysis will be described in the SAP. Any

This document is confidential.

Page 74 of 89

MetrioPharm AG	MP1032-CT05
MP1032	Protocol v2.0 - Bulgaria

possible correlation between plasma exposure and biomarkers (eg, change from baseline in cytokines, or other coagulation/inflammatory biomarkers) or efficacy measures can be explored by appropriate regression analysis methods during the final data analysis.

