- Proportion of patients with disease resolution on Day 14. Disease resolution is defined as patients who are alive and have a score of 6, 7, or 8 on the NIAID 8-point ordinal scale.
- All-cause mortality rate at Day 14 and Day 60
- Change of clinical status related to COVID-19 on Day 14 compared with baseline according to the NIAID 8-point ordinal scale as listed above
- Proportion of patients requiring invasive ventilation (mechanical ventilator and/or ECMO), or who are not alive on Day 14 or Day 28
- Proportion of patients in each category of the NIAID 8-point ordinal scale
- Time to (first) improvement of at least 1 category on the NIAID 8-point ordinal scale (until Day 28). Patients who did not improve at least 1 category on the NIAID scale or die before Day 28 will be censored at Day 28.
- The odds ratio between MP1032 and SoC and placebo and SoC for the number of patients with clinical status improvement from baseline on the NIAID 8-point ordinal scale (ie, an improvement of at least 1 category) at Day 14 and Day 28
- Total duration of hospitalization on Day 28 and Day 60 (from baseline to discharge; with death censored on the last day of the observed period at Day 28 or Day 60, respectively)
- Proportion of patients alive and testing negative for COVID-19 on Day 14, Day 28, and Day 60

This document is confidential.

Page 32 of 80

- Safety and tolerability assessed by:
 - Cumulative incidence of TEAEs (summarized by seriousness, severity, relationship to the study medication, outcome, and duration)
 - Vital sign parameters
 - Clinical laboratory parameters
 - Physical examination findings
- MP1032 plasma concentrations and PK parameters (if possible) including maximum observed plasma concentration, area under the concentration-time curve, elimination parameters, apparent body clearance, apparent volume of distribution, trough concentration, average observed plasma concentration at steady state, and other relevant PK parameters assessed via MP1032 plasma exposure on Day 1 and Day 7 in a PK subset of patients

Exploratory endpoints of this study are:

- Change in saturation of oxygen (SpO₂)/fraction of inspired oxygen (FiO₂) ratio (for patients alive) on Day 14 or Day 28 compared with baseline
- Total number of days in the intensive care unit (ICU)
- Duration of invasive mechanical ventilation
- Duration of ECMO

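### Bulgarian Table 1, footnote m, lists 14 PK draws but states 16: the 120-minute sample in Section 13.1 is missing

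*Protocol*

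**What the plan says.** **Bulgaria v2.0, Table 1, footnote m.** Draws on Days 1 and 7 are predose and "postdose at 10 minutes, 20 minutes, 30 minutes, 60 minutes, 8 hours (before next dose), and 24 hours". The same footnote states: "A total of 16 samples will be collected relative to the first dose on Day 1 and the first dose on Day 7".

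**Bulgaria v2.0, Section 13.1 (Pharmacokinetic Sampling).** The list is predose and "postdose at 10 minutes, 20 minutes, 30 minutes, 60 minutes, 120 minutes, 8 hours (before next dose), and 24 hours". The total is again 16, with "approximately 4.9 mL per time point for a total of approximately 78.4 mL". The section opens by saying that samples "will be collected at the time points indicated in the Schedule of Assessments (Table 1").

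**Bulgaria v2.0, Section 10.2.** Assessments and their timing follow Table 1.

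**France v2.0.** The synopsis, Table 1 footnote n and Section 13.1 all include the 120-minute draw.

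**Section 15.5.** PK parameters on each day, "using up to 8 hours postdose, will be derived applying noncompartmental analysis". The PK endpoints in Section 6.2 (seen in the French version) include AUC and "elimination parameters, apparent body clearance, apparent volume of distribution", with the qualifier that they are derived if possible.

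**The concern.** The Bulgarian protocol gives two sampling lists for one PK profile, and the shorter one does not add up to its own total. The shorter list also sits in the table to which Sections 10.2 and 13.1 refer the reader for timing.

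The missing time is the only planned one between 1 and 8 hours. Because the analysis stops at 8 hours, a patient sampled by footnote m would contribute predose, 10, 20, 30 and 60 minutes, and then 8 hours. AUC would have to cross seven hours in one step, or stop at 1 hour instead of 2 if the 8-hour level cannot be quantified. One of the few points after the peak would also usually go. A missed timed draw cannot be recovered later.

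**Working it through.** **1. Count and volume.** Inputs are the two lists above and 4.9 mL per draw (Section 13.1).

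| List | Draws per day | × 2 days | × 4.9 mL |
|---|---|---|---|
| Section 13.1, with 120 minutes | 8 | 16 | 78.4 mL |
| Footnote m, without it | 7 | 14 | 68.6 mL |

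The plan's own figures, 16 samples and 78.4 mL, come out exactly from Section 13.1. They do not come out from footnote m. The error is therefore in the footnote's list, not in the total.

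**2. What is left up to 8 hours.** Footnote m gives 0, 1/6, 1/3, 0.5, 1 and 8 h. Section 13.1 gives the same times plus 2 h. The 24-hour draw lies outside the analysis window. The 120-minute limit on eating after a dose, for PK patients, is a food rule and not a draw.

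**3. How much the 2-hour point could matter.** The protocol gives no half-life, absorption rate or trapezoid rule, so these are assumed scenarios. The model is one-compartment oral after a single dose: C(t) = ka/(ka − k) × (exp(−kt) − exp(−ka·t)), with k = ln 2 / half-life. Each cell compares the trapezoidal AUC from 0 to 8 h with the exact value, without / with the 120-minute sample.

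| ka | Half-life | Linear error | Linear-up/log-down error | Points after observed peak |
|---|---|---|---|---|
| 4/h | 1 h | +82% / +34% | −3% / −1% | 2 / 3 |
| 4/h | 2 h | +31% / +17% | −2% / −1% | 2 / 3 |
| 4/h | 4 h | +8% / +5% | −1% / −1% | 1 / 2 |
| 4/h | 8 h | +1% / +1% | −1% / 0% | 1 / 2 |
| 2/h | 1 h | +67% / +37% | −11% / −3% | 1 / 2 |
| 2/h | 2 h | +19% / +16% | −9% / −2% | 1 / 2 |
| 2/h | 4 h | −0.3% / +4% | −7% / −2% | 1 / 2 |
| 2/h | 8 h | −5% / +0.2% | −7% / −1% | 1 / 1 |

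In the last row the 2-hour sample is itself the observed peak, so dropping it moves the observed peak from 2 h to 1 h and leaves the post-peak count unchanged.

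**4. If the 8-hour level is not quantifiable** (ka 4/h, half-life 1 h), AUC to the last measurable sample covers 40% of the 0–8 h area when that sample is at 1 h, and 70% when it is at 2 h.

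**The case against.** The intended schedule is hardly in doubt. Footnote m itself says 16, and Section 13.1 prints the full list with a volume that fits only 16 draws. Section 13.1 also leaves the details of PK collection and the time windows to a laboratory manual that is not shown and may list 120 minutes. Only part 2 of the Bulgarian protocol is available, so its synopsis cannot be checked. The clarification memo at hand is numbered 2 and deals with overdose; memo 1 is not shown. All of this stands. It makes the loss conditional, but the protocol would still contradict itself.

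Several stronger readings are tempting, and the documents do not support them:

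- **That the omission is what prevents a three-point terminal slope.** In the table, the full schedule reaches three post-peak points only at ka 4/h with half-lives of 1 or 2 h. In the other six scenarios it gives two or fewer. That is mostly a consequence of the planned sparse sampling, and the endpoint is worded as if possible.
- **That AUC would be badly biased.** The 82% needs a 1-hour half-life and the linear rule. With log-down at ka 4/h the error is at most 3%, and at ka 2/h with a 4-hour half-life the linear error is smaller without the sample.
- **That the roughly 20 active profiles would differ by country.** The protocol does not say how many PK patients, if any, are Bulgarian. PK consent is optional, and about 40 sites are planned worldwide.
- **That this is a fault in the analysis method.** It is an inconsistency in a sampling schedule.

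**Conclusion.** Footnote m is wrong as written: 14 draws listed against 16 stated, with the 120-minute sample missing. That conclusion rests on a count alone and needs no assumption.

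The consequence is conditional. If a Bulgarian site draws by footnote m, that patient has no sample between 1 and 8 hours. This can degrade AUC to the last measurable sample and usually removes one of few post-peak points. The size, from negligible to large, cannot be fixed from this document because it depends on unstated kinetics and an unstated AUC rule. Only secondary PK endpoints in the PK subset are exposed; efficacy and safety analyses are not. Severity is minor, but the point is worth correcting because the draw cannot be recovered and the correction is nearly free.

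**What to change.** In Bulgarian Table 1, footnote m, insert 120 minutes between 60 minutes and 8 hours. The footnote then lists 8 draws a day and agrees with its own total, with Section 13.1 and with 78.4 mL.

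Section 16.7.1 treats corrections of typographical errors as administrative amendments, sent to the ethics committee for information only. A clarification memo, a route the sponsor has already used for the overdose definition, can tell Bulgarian PK sites at once. No blood is needed beyond the volume already stated. Profiles already drawn without the sample cannot be repaired, so flag them wherever AUC and elimination parameters are summarized.

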10.2 Study Procedures

Assessments and their timing are to be performed as outlined in the Schedule of Assessments (Table 1). Section 12.5 specifies clinical laboratory assessment samples to be obtained.

Assessments and procedures scheduled at a visit where study drug is administered should be performed before administration of treatment unless otherwise indicated in the Schedule of Assessments (Table 1).

Efficacy assessments are described in Section 11 and include COVID-19 symptoms, COVID-19 severity, clinical status related to COVID-19 on the NIAID 8-point ordinal scale, HRQoL assessed by the EQ-5D-5L questionnaire (Appendix 2), and COVID-19 testing.

Safety assessments are described in Section 12 and include medical/surgical history and demographics, vital signs, physical examinations, ECGs, clinical laboratory assessments, and AEs. PK assessments are described in Section 13 and include PK sampling and PK analytical methodology. Biomarkers are described in Section 14.1.

The investigator may, at his/her discretion, arrange for a patient to have an unscheduled assessment, especially in the case of AEs that require follow-up or are considered by the investigator to be possibly related to the use of study drug. The unscheduled visit page in the eCRF must be completed.

Procedures for early study withdrawal are described in Section 8.4.

1 EFFICACY ASSESSMENTS

The Schedule of Assessments (Table 1) outlines the efficacy assessments to be performed throughout the study and their timing.

This document is confidential.

Page 53 of 89

MetrioPharm AG	MP1032-CT05
MP1032	Protocol v2.0 - Bulgaria

1 COVID-19 Symptoms

The assessment of the COVID-19 symptoms will be recorded at the visits specified in the Schedule of Assessments (Table 1).

The patient will be assessed for the following as shown in Table 2.

Table 2COVID-19 Symptoms

Symptom	Response Options and Scoring
1. Stuffy or runny nose	
2. Sore throat	
3. Red or irritated eyes (conjunctivitis)	
4. Shortness of breath (difficulty breathing)	
5. Cough	None = 0
6. Low energy or tiredness	Mild = 1
7. Muscle or body aches	Moderate = 2 Severe =3
8. Headache	Severe -5
9. Chills or shivering	
10. Feeling hot or feverish	
11. Nausea (feeling like you wanted to throw up)	
12. How many times did you vomit (throw up) in the last 24 hours?	I did not vomit at all = 0 1-2 times = 1 3-4 times = 2 5 or more times = 3
13. How many times did you have diarrhea (loose or watery stools) in the last 24 hours?	I did not have diarrhea at all = 0 1-2 times = 1 3-4 times = 2 5 or more times = 3
14. Rate your sense of smell in the last 24 hours.	My sense of smell is THE SAME AS usual = 0 My sense of smell is LESS THAN usual = 1 I have NO sense of smell = 2
15. Rate your sense of taste in the last 24 hours.	My sense of taste is THE SAME AS usual = 0 My sense of taste is LESS THAN usual = 1 I have NO sense of taste = 2

Note: Score values are included in the table for ease of reference. Score values within the response options will not be presented to patients to avoid confusing patients.

12 COVID-19 Severity

The assessment of the COVID-19 severity will be recorded at the visits specified in the Schedule of Assessments (Table 1). As per the inclusion and exclusion criteria (see Section 8.1 and Section 8.2), patients who are randomized must have either moderate or severe COVID-19. The criteria (FDA 2020) used to determine the patient's COVID-19 severity incorporates objective measures as follows:

MetrioPharm AG	MP1032-CT05
MP1032	Protocol v2.0 - Bulgaria

MP1032-CT05

Final

Asymptomatic SARS-CoV-2 infection

- Positive SARS-CoV-2 testing by standard RT-PCR assay or equivalent test
- No symptoms

Mild COVID-19

- Positive SARS-CoV-2 testing by standard RT-PCR assay or equivalent test
- Symptoms of mild illness with COVID-19 (eg, loss of smell or taste, fever, cough, sore throat, malaise, headache, muscle pain, gastrointestinal symptoms, and without shortness of breath or dyspnea)
- No clinical signs indicative of moderate, severe, or critical COVID-19

Moderate COVID-19

- Positive SARS-CoV-2 testing by standard RT-PCR assay or equivalent test
- Symptoms of moderate illness with COVID-19, which could include any symptom of mild illness or shortness of breath with exertion
- Clinical signs suggestive of moderate illness with COVID-19, such as respiratory rate ≥20 breaths per minute, SpO₂ >93% (on room air at sea level, if possible), heart rate ≥90 beats per minute
- No clinical signs indicative of severe or critical COVID-19

Severe COVID-19

- Positive SARS-CoV-2 testing by standard RT-PCR assay or equivalent test
- Symptoms suggestive of severe systemic illness with COVID-19, which could include any symptom of moderate illness or shortness of breath at rest, or respiratory distress
- Clinical signs indicative of severe systemic illness with COVID-19, such as respiratory rate ≥30 breaths per minute, heart rate ≥125 beats per minute, SpO₂ ≤93% (on room air at sea level, if possible), PaO₂/FiO₂ <300, or diagnosed with ARDS (according to the Berlin definition; see Table 3 for further details)
- No criteria for critical COVID-19

Critical COVID-19

- Positive SARS-CoV-2 testing by standard RT-PCR assay or equivalent test
- Evidence of critical illness, defined by at least 1 of the following:
 - Respiratory failure defined based on resource utilization requiring at least 1 of the following:
 - Endotracheal intubation and mechanical ventilation, oxygen delivered by high-flow nasal cannula (heated, humidified, oxygen delivered via reinforced nasal cannula at flow rates >20 L/min with fraction of delivered oxygen ≥0.5), non-invasive positive pressure ventilation, ECMO, or clinical diagnosis of respiratory failure (ie, clinical need for 1 of the

This document is confidential.

Page 55 of 89

MetrioPharm AG	MP1032-CT05
MP1032	Protocol v2.0 - Bulgaria

preceding therapies, but preceding therapies not able to be administered in setting of resource limitation)

- Shock (defined by systolic blood pressure <90 mm Hg, or diastolic blood pressure <60 mm Hg or requiring vasopressors)
- Multi-organ dysfunction/failure

A clinical diagnosis of respiratory failure (in the setting of resource limitation) in which the management deviates from SoC must be recorded.

To standardize the assessment of COVID-19 severity, respiratory rate, SpO_2 , and heart rate will be measured when the patient is on room air at sea level (ie, no supplemental oxygen, if possible) and at rest for at least 5 minutes. If possible, the site should collect the information from each patient at the same time each day (± 1 hour).

Please note: Patients who are receiving oxygen therapy at baseline for a chronic condition (eg, emphysema, COPD, PAH, IPF, etc) must be considered as having severe COVID-19 (unless the patient meets the definition for critical COVID-19). For questions related to COVID-19 severity, the investigator should contact the medical monitor.

Timing	Within 1 week of known clinical insult or new or worsening respiratory symptoms		
Chest imaging ^a	Bilateral opacities — not fully explained by effusions, lobar/lung collapse, or nodules		
Origin of edema	Respiratory failure not fully explained by cardiac failure or fluid overload. Need objective assessment (eg, echocardiography) to exclude hydrostatic edema if no risk factor is present		
Oxygenation ^b	Mild	200 mm Hg < $PaO_2/FIO_2 \le 300$ mm Hg with PEEP or CPAP ≥ 5 cmH ₂ O ^c	
	Moderate	100 mm Hg < $PaO_2/FIO_2 \leq 200$ mm Hg with PEEP ≥ 5 cmH ₂ O	
	Severe	$PaO_2/FIO_2 \le 100 \text{ mm Hg with PEEP} \ge 5 \text{ cmH}_2O$	

 Table 3:
 Acute Respiratory Distress Syndrome – Berlin Definition

Abbreviations: ARDS = acute respiratory distress syndrome; CPAP = continuous positive airway pressure; FIO₂ = fraction of inspired oxygen; PaO₂ = partial pressure of arterial oxygen; PEEP = positive end-expiratory pressure.

- a Chest radiograph or computed tomography scan
- b If altitude is higher than 1,000 m, the correction factor will be calculated as follows: [PaO₂/FIO₂ (barometric pressure/760)]
- c This may be delivered noninvasively in the mild ARDS group

Source: Adapted from Fanelli et al 2013.

13 Clinical Status Related to COVID49 on the National Institute of Allergy and Infectious Diseases 8-Point Ordinal Scale

The NIAID 8-point ordinal scale is an assessment of the clinical status at the first assessment of a given study day. The scale is as follows:

1. Death

This document is confidential.

MP1032-CT05

Final

MetrioPharm AG	MP1032-CT05
MP1032	Protocol v2.0 - Bulgaria

- 2. Hospitalized, on invasive ventilation (mechanical ventilator and/or ECMO)
- 3. Hospitalized, on non-invasive ventilation or high-flow oxygen devices
- 4. Hospitalized, requiring supplemental oxygen
- 5. Hospitalized, not requiring supplemental oxygen but requiring ongoing medical care (COVID-19 related or otherwise)
- 6. Hospitalized, not requiring supplemental oxygen and no longer requires ongoing medical care (used if hospitalization was extended for infection-control reasons)
- 7. Not hospitalized, limitation on activities, and/or requiring home oxygen
- 8. Not hospitalized, no limitations on activities

Please note: Patients requiring oxygen before COVID-19 and returning to baseline oxygen use will be considered improved (ie, not requiring supplemental oxygen). Patients with a limitation on activities before COVID-19 and returning to baseline activity will be considered improved.

At the visits specified in the Schedule of Assessments (Table 1), record the date and time for each individual component of the NIAID 8-point ordinal scale including: invasive or non-invasive mechanical ventilation/ECMO start/stop, high-flow/mask oxygen start/stop, supplemental oxygen start/stop (nasal cannula, liter flow [and its conversion to FiO_2], other delivery services), hospital discharge (whether with limitations or without limitations), hospitalization type (eg, transfer to ICU) start/stop, and (if applicable) death, cause of death (including relatedness to COVID-19), and date/time of death. If possible, the site should collect the information from each patient at the same time each day (± 1 hour).

A standard conversion for liter flow oxygen to FiO₂ is presented in Table 4.

	FiO ₂ (%)
Room air	21
1 L/min	24
2 L/min	27
3 L/min	30
4 L/min	33
5 L/min	36
6 L/min	39

Table 4Standard Conversion for Liter Flow Oxygen

If there is use of a venturi mask (air-entrainment mask), the FiO_2 is based on the nozzle use and should also be recorded.

This document is confidential.

Page 57 of 89

14 Health-related Quality of Life Assessment

The HRQoL will be assessed via the EQ-5D-5L questionnaire (Appendix 2). The EQ-5D-5L is a standardized questionnaire developed by the EuroQol Group as a measure of HRQoL that consists of a descriptive system and a VAS. The descriptive system consists of 5 dimensions: mobility, self-care, usual activities, pain/discomfort, and anxiety/depression. The VAS records the patient's self-rated health on a vertical VAS. This can be used as a quantitative measure of health outcome that reflects the patient's own judgment. The patient is asked to indicate his/her current health state (ie, describe their health "today"). The scores on these 5 dimensions can be presented as a health profile or can be converted to a single summary index number that describes the patient's current health state. The EQ-5D-5L questionnaire has been validated in a diverse patient population in 6 countries and is available in multiple languages. The EQ-5D-5L questionnaire is suitable for completion by adults (EuroQol Research Foundation 2020).

The results of the EQ-5D-5L questionnaire will be recorded at the visits specified in the Schedule of Assessments (Table 1). Please note: This assessment will only be performed in patients who have been discharged from the hospital before Day 60.

15 COVID-19 Testing

Samples for COVID-19 testing will be obtained at the visits specified in the Schedule of Assessments (Table 1). At the screening visit, the local laboratory may perform COVID-19 testing by standard RT-PCR assay or equivalent test. At screening, a positive test must be available in order for the patient to be randomized on Day 1. If the patient has a previous confirmation of SARS-CoV-2 (within 7 days of Day 1), the SARS-CoV-2 test at screening is not required. The result of the COVID-19 tests (positive/negative) must be documented in the eCRF

On Day 1, Day 14, Day 28, and Day 60, samples will be sent to the central laboratory for COVID-19 testing by standard RT-PCR assay. The result of the COVID-19 tests (positive/negative) must be documented in the eCRF. Further details will be described in the laboratory manual.

Please note: If COVID-19 tests are performed at unscheduled time points (eg, according to SoC), findings (ie, positive/negative result) must be recorded in the eCRF.

